12.0 Study Design/Procedures

- 1) Describe the overall study design (e.g.: single visit, single-blind, double-blind, non-randomized, randomized, blood draw, investigational drug, device etc.).
- 2) Provide a description of all study-related research procedures being performed, including the length of time involved.
- 3) Include procedures being performed to monitor research participants for safety or minimize risks.

HRP- 503SBER	TEMPLATE: CWRU SBER Protocol		
Approved:	09/2021	Prior Version:	05/2021

- 4) Describe the source records including medical or educational records, which will be used to collect data about subjects.
- 5) Include a description of any device being used to collect data (e.g., eye tracker, step counter). If the device itself is being studied, include additional information in Section 29.

Overall Study Design. We propose to conduct a single-arm pre- and post-test intervention study to evaluate the preliminary efficacy, as well as the acceptability and feasibility of the KINDER program. Participation includes completion of a 9-week intervention, as well as completion of two surveys (baseline and follow up). Total study participation is estimated to take 20 hours depending how long it takes caregivers to complete lessons and will be spread over 3 months. Intervention. KINDER is a 9 week digitally delivered psychoeducational intervention to promote healthy caregiving relationships by building caregiver resourcefulness, for the purpose of improving quality of care and preventing verbal elder mistreatment. Content includes a mix of synchronous and asynchronous activities, including three 1.5-hour group facilitated Discussion Sessions by Zoom, 3 check in calls with a facilitator of approximately 20 minutes each, and 8 independent lessons consisting of a story-based video, reading, reading quiz, reflection, and self-care goal. Lesson topics include understanding a dementia diagnosis, communicating with person you care for about challenging topics, finding a balance between safety concerns and independence, and more. Each lesson takes an estimated 1 hour to complete. Independent KINDER lessons can be completed using a printed or digital copy of the KINDER Workbook. Interventionist Training. Interventionists will undergo at least 2 hours of didactic training, in addition to selfstudy and shadowing or co-facilitating Discussion Sessions. Didactic training will include a review of the KINDER program and its underlying theory, review of the workbook and discussion sessions, and review of the facilitator guide. Didactic sessions will include active learning components, such as role-play of facilitator calls to participants. Before delivering sessions independently, facilitators will either shadow or co-facilitate KINDER sessions with another trained facilitator or the PI. Screening and Enrollment. Participants may complete eligibility online or by phone. If a participant completes the eligibility screening online and is eligible, they will receive a telephone follow up call from the study team member notifying them. (If the participant is not eligible following screening, they will receive an email notification.) During this call, the study team member will review the consent form with the participant and answer any questions they may have. If the caregiver would like to participate, they will be sent an email with a link to the consent form to complete. Interested caregivers who complete the eligibility screening by phone will undergo the same process, except the screening call will also include review of information in the consent form if the participant is eligible. **Recruitment.** Participants will primarily be recruited by contacting those caregivers who register to participate in KINDER on Eventbrite. Caregivers will be asked to indicate whether they would like to be contacted by researchers about a study on the KINDER program. The research team will then follow up to provide more information, altering between phone and email. (See Participant Communications.) Other methods of

HRP- 503SBER	TEMPLATE: CWRU SBER Protocol		
Approved:	09/2021	Prior Version:	05/2021

recruitment include sharing flyers at community organizations and Facebook social media posts. Data Collection. Data collection will be primarily conducted in REDCap using self-administered surveys. A baseline survey will be sent within 2 weeks of the caregiver attending Discussion Session 1. The follow up survey will be sent immediately following completion of the intervention. Participants will receive up to 3 reminders to complete surveys. Caregivers who attend KINDER who do not participate in the study will also be invited to complete an anonymous satisfaction survey via REDCap. In addition to participant surveys, we will also ask facilitators, who are not members of the study team, to complete a facilitator monitoring report, call logs, and participant attendance forms to monitor adherence to protocols and intervention exposure. An observer from the study team will also complete a fidelity monitoring report using recorded discussion sessions. Some participants will also be asked to participate in a one-on-one semi-structured qualitative interview by phone or Zoom so we can learn more about experiences participating in KINDER. Participants will be purposefully selected, so as to ensure the representation of caregivers from various demographic backgrounds and caregiving situations. Further, we will send a satisfaction survey to all KINDER participants to learn more about their experiences participating in the program to support its ongoing improvement. For those who do not attend any or <2 discussion sessions, we will also send a survey asking about reasons for non-participation. Safety Monitoring. The PI will complete a safety monitoring report once every 3 months of this study. Information will include the number of individuals recruited, enrolled, dropped out, demographic information on participants, and descriptive information on study variables including the proportion of missing data for each variable.

13.0 Study Timeline (optional)

	Pre-	Visit	Visit	Visit	Six week Follow
	Screening	1	2	3	up
Estimated time requirement of					
visit					
Data Collection					
Study Procedure 1					
Study Procedure 2					
Study Procedure 3					
Phone Call Questionnaire					

14.0 ClinicalTrials.gov Information

Directions: If this study has been registered on ClinicalTrials.gov, provide the ClinicalTrials.gov identifier and the investigator/sponsor responsible for registering. If this study has not been registered on ClinicalTrials.gov, provide the rationale as to why and

HRP- 503SBER	TEMPLATE: CWR	U SBER Protoc	ol
Approved:	09/2021	Prior Version:	05/2021

if/when it will be. If it does not meet the requirement for being registered on ClinicalTrials.gov, please state that.

This study is registered on ClinicalTrials.gov at NCT05783102.

15.0 L	ist of l	Data	to be	Coll	lected
--------	----------	------	-------	------	--------

1.	Indicat	ate what identifiers you will collect	
	\boxtimes	Name	
	\boxtimes	Address (e.g., Zip code, other geographical designation, etc.)	
		Dates related to an individual (e.g., Date of admission, birth, surgery, etc.)	
	\boxtimes	Telephone number	
		Fax number	
	\boxtimes	Email address	
		Social security number	
		Medical record number	
		Health plan beneficiary number	
		Account number	
		Certificate/license number	
		Any vehicle or other device serial	
		Device identifiers or serial numbers	
		Web URL	
		Internet protocol (IP) address	
		Finger or voice prints (includes audio recordings)	
		Photographic images (includes video recordings)	
		Other: Any characteristic that would uniquely identify the individual	
		If other, please explain: Click here to enter text.	

2. List all other data to be collected for the research study. Attach all data collection tools on the Local Site Documents page of the SpartaIRB smart form (Other Attachments). **Eventbrite Registration:** Name, email, phone number, mailing address, year born, gender, race, ethnicity, education, financial strain. (Participants are notified that demographic information is optional to provide and will be used by the study team.) **Screening:** Year born, caregiving status, hours of caregiving, access to technology, care recipient functional ability, plans for nursing home placement, name, email, phone number. Interested participants are notified that they may also provide demographic information to help the study team understand differences between those eligible and ineligible for participation. These items are consistent with those required by the NIA CROMS data collection items: biological sex, gender identity, sexual orientation, race, ethnicity, highest level of education, marital status, financial strain, kin relationship to care recipient, primary language. Off-Study Reason. Reason for withdrawing from study; reason for ending intervention participation **Baseline Demographic Information**: Year born, gender identify, race, ethnicity, marital status, education, current employment, financial strain, kin relationship to care recipient, primary care status, living situation

HRP- 503SBER	TEMPLATE: CWRU SBER Protocol		
Approved:	09/2021	Prior Version:	05/2021

with care recipient, length of care, weekly hours of care. **Baseline and Follow Up Survey Measures:** Revised Memory and Behavior Checklist, Dyadic Relationship Scale, Depressive Cognitions Scale, Relational Certainty, Resourcefulness, Caregiver Self-Efficacy Scale-8, Modified Conflict Tactics Scale, Task Management Scale Index, Exemplary Care Scale. **Satisfaction:** Satisfaction with the KINDER program and components **Reason for non-participation.** Reason the registered individual did not attend KINDER or attended <2 sessions. **Facilitator Call Log:** Completion of facilitator calls with participants **Facilitator Fidelity Form:** Name of facilitator and session date, perception of sessions (e.g., participant engagement, adherence to session agenda), participant attendance

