2.0 Objectives

Directions: Describe the purpose, specific aims or objectives. Be sure to also include the hypothesis being tested. Aim 1: Test the preliminary efficacy of KINDER. The investigators hypothesize caregivers will report improved resourcefulness (mediator for future study) and relationship quality (primary outcome) following participation. Further, caregivers will report higher quality of care and reduced frequency of verbal mistreatment (distal outcomes). **Aim 2:** Determine acceptability among caregivers and feasibility with satisfaction surveys and fidelity reports.

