4.0 Inclusion and Exclusion Criteria

Directions: Describe how individuals will be screened for eligibility.

Participants may complete eligibility screening by phone or begin the screening online. Participants who complete screening online will receive a telephone follow up to complete any questions they may have missed and answer questions they may have.

Using the tables below, describe the inclusion and exclusion criteria that will define who will be included and excluded in your final study sample.

	Inclusion		
1.	Is age 18+		
2.	Provides care to a family member or friend living with Alzheimer's Disease or a		
	related dementia. This does not have to be diagnosed.		
3.	Participant helps with at least 1 activity of daily living (e.g., bathing) or 2 instrumental		
	activities of daily living (e.g., shopping)		
4.	Participant provides at least 8 hours of assistance to the care recipient per week		
5.	Participant does not intend to place the care recipient in a skilled nursing facility		
	within 3 months of consenting into the study		

		Exclusion
	1.	Does not read and speak English
ſ	2.	Does not have reliable access a computer and internet

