10.0 Consent Process

Indicate	whether	von '	will	he ob	taining	consent:
muncacc	************	1 U U	** **	nc	tamme	COMSCIIC.

⊠ Yes □ No

If yes, answer the following questions:

- 1. Describe who will consent the subjects and where the consent process will take place: The principal investigator will review the consent document with participants by telephone after confirming participant eligibility either online or by phone. The participant will then receive an email with a link to the downloadable consent document. The participant will be able to open a PDF version of the consent document and will be asked to provide their electronic signature their consent to participate in REDCap. They will receive an email confirmation of consent with a copy of the consent form attached.
- 2. The time that will be devoted to the consent discussion: Based on experience with prior protocols using a similar approach, it is estimated that the consent discussion will take approximately 15 minutes to complete by phone. Participants may also take as long as they wish while the study is ongoing to review and sign the consent form. If it has been more than 2 months since a caregiver completed eligibility screening when the consent form is returned, they will be rescreened to ensure ongoing eligibility.
- 3. Any waiting period available between informing the prospective subject and obtaining the consent: Participants are allowed to request time to think about

HRP- 503SBER	TEMPLATE: CWRU SBER Protocol		
Approved:	09/2021	Prior Version:	05/2021

enrolling in the study after learning they are eligible. We will share that this option while completing the consent process.

- 4. Steps that will be taken to ensure the research participants' understanding: The PI will check with the participant to ask if they have any questions about the information provided while describing each section of the consent form. Important information, such as that participation in the study is voluntary and researchers' obligation to report suspected mistreatment, will be emphasized to ensure participants understand these important points. The PI will also listen for signs that the participant does not understand the information shared correctly. Further, participants are asked to answer questions about the study consent form before signing. Caregivers will not be able to sign the consent form until questions are correctly answered.

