23.0 Withdrawal of Research Participants

Directions: Describe the anticipated circumstances under which research participants will be withdrawn from the research without their consent. Also include the procedures that will be followed when a research participant withdraws or are withdrawn from the research, including partial withdrawal from procedures with continued data collection. Participants may be withdrawn from the study if they 1) do not complete the baseline survey or 2) miss 2 or more group-based sessions. Participants may continue to participate in the KINDER program if this occurs but will be removed from the study. If this does occur, the PI will send an email to the participant to notify them. We will keep all data collected until withdrawal unless asked not to by a participant. We will attempt to contact participants to learn about their reason for withdrawal. See "Call Scripts for Caregivers Who Go Off Protocol"

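### No follow-up item records whether the participant is still caring or how many hours they give, so lost contact with the care recipient can be counted as a KINDER effect on mistreatment or care quality

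*Combined protocol and SAP*

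**What the plan says.** **Outcomes.** Section 2.0 expects that "caregivers will report higher quality of care and reduced frequency of verbal mistreatment (distal outcomes"). Relationship quality is the primary outcome.

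**What is recorded, and when (Section 15.0).**
- Screening takes "Year born, caregiving status, hours of caregiving, access to technology, care recipient functional ability, plans for nursing home placement".
- The baseline demographic list includes "kin relationship to care recipient, primary care status, living situation" and continues "with care recipient, length of care, weekly hours of care".
- The list for both baseline and follow-up names nine scales. None is named as a measure of hours of care, living situation, placement or death.
- An off-study item records why someone left the study or ended the intervention. A separate survey asks why a registrant attended no session or fewer than two.

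**Who stays in.** Under Section 23.0 participants may be withdrawn if they "do not complete the baseline survey or 2) miss 2 or more group-based sessions". Section 12.0 sends the follow-up survey at the end of the 9-week programme, with up to 3 reminders.

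**Entry criterion.** Section 4.0 requires: "Participant does not intend to place the care recipient in a skilled nursing facility" within 3 months of consent.

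**Analysis.** Section 17.0 compares pre and post means by paired t-test. Section 12.0 describes a single arm. Section 5.0 plans 34 analysed out of 46 enrolled, with a one-sided test at 0.05.

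**The concern.** How often a caregiver speaks harshly to a relative depends partly on how much time they spend together. If the relative dies or moves into residential care, or someone else takes over, the reported frequency can fall with no change in the caregiver's behaviour. Care-quality answers may also stop describing current care.

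In a controlled trial such events would occur in both arms. Here the pre–post difference is the whole estimate, and the planned surveys name nothing that would identify the affected participants. Preventing verbal mistreatment is the programme's stated purpose, and Section 3.0 says the findings will inform later efficacy testing, so a spurious signal would carry forward. The information cannot be recovered from the planned surveys afterwards.

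**Working it through.** **1. Can an affected caregiver reach the analysis?** There are three Discussion Sessions, in weeks 1, 5 and 9. Suppose care ends after the week 5 session.
- If the caregiver attends week 9, no session is missed and no withdrawal rule applies.
- If they skip week 9, one session is missed. The withdrawal rule needs two, and the non-participation survey goes to those who attended fewer than two.

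Either way the person can remain in the study and be sent the follow-up survey, for which Section 26.0 pays $75. An off-study reason would be recorded only if they withdrew or ended the intervention.

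**2. The planned sample size.** For a paired t-test with an assumed standardised effect of 0.5, alpha 0.05 and power 0.80, exact noncentral-t power gives 34 pairs two-sided (power 0.808) and 27 one-sided. So 34 reproduces at 0.5 only as a two-sided figure. That is a separate matter; here 34 is simply the number of pairs. The allowance for loss is 1 − 34/46 = 26%.

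**3. Size on mistreatment frequency.** The documents give no rate of placement, death or reduced care, so these inputs are assumptions:
- no programme effect; 34 pairs; one-sided paired t-test at 0.05;
- one-third to two-thirds of caregivers report any mistreatment (the range in Section 3.0, used here as the share with non-zero rates);
- counts for those caregivers are Poisson, with gamma-distributed rates of mean 4 and shape 1 or 2; the rest are zero;
- the follow-up rate is multiplied by 0 if care stopped, 0.5 if contact halved and 1.5 if contact rose by half.

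Expected fall in mean frequency = share stopping + 0.5 × share halving − 0.5 × share rising.

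| Assumed change by follow-up | Fall in mean | False-positive rate |
|---|---|---|
| None | 0 | 0.05 |
| 3% stop (34 × 0.03 ≈ 1 person) | 3% | 0.06–0.07 |
| 6% stop (34 × 0.06 ≈ 2 people) | 6% | 0.07–0.09 |
| 3% stop, 10% halve | 3 + 5 = 8% | 0.08–0.12 |
| 6% stop, 20% halve | 6 + 10 = 16% | 0.14–0.25 |
| 12% stop, 20% halve | 12 + 10 = 22% | 0.18–0.35 |
| 6% stop, 20% halve, 20–30% rise by half | 6 + 10 − 10 = 6% to 6 + 10 − 15 = 1% | about 0.05–0.10 |

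**4. Cross-check with a simpler model.** Take normal changes with SD 1, and let each affected caregiver's score fall by 1 to 2 SD. One affected caregiver in 34 gives 0.07–0.08 and two give 0.09–0.12. This is the same order as the rows where care only stops.

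**5. Reading the table.** The stop-only rows need just one or two people. The large figures appear only when contact also falls, on balance, among those still caring. Nothing in the documents supports or excludes that.

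**The case against.** **Some affected caregivers would be identified.** One whose relative dies or is placed may stop attending, miss two sessions and be asked why; Section 17.0 reports those reasons. Facilitator calls could also bring the event to light. This stands, and limits the problem to those who stay in.

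**The fall in score is an inference.** The recall period and scoring of the Modified Conflict Tactics Scale are not shown. If recall reaches back before the event, the drop is smaller than the zero multiplier assumes. The survey forms are separate attachments, so a care-status branch might exist there. The repeated Memory and Behavior Checklist and Task Management Scale Index might also partly reflect changed care. These points stand: the effect can occur but is not certain.

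**The bias need not always favour KINDER.** A person with dementia may come to need more care as easily as less. This stands for partial changes. A reader might infer from the 0.14–0.35 rows that serious inflation is to be expected, but those rows rest on a one-directional drop in contact that no section supports.

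**The placement criterion.** A reader might also infer that it is bound to lapse before follow-up, since consent may follow screening by some time: "If it has been more than 2 months since a caregiver completed eligibility screening when the consent form is returned, they will be rescreened". The documents do not support that. Three months is about 91 days, and 91 − 63 = 28 days remain for the wait before Session 1 and the survey response; Section 12.0 plans 3 months of participation. A lapse is possible but not built in. Nor is it needed for the point, because an intention stated at entry cannot cover death or unplanned placement.

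**Weight.** Mistreatment and care quality are distal outcomes in a pilot. That keeps the point modest but does not remove it, because the remedy is cheap.

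**Conclusion.** The gap is real. As listed, the data cannot separate less mistreatment, or changed care quality, from less contact among participants who stay in the study, and a single-arm paired comparison offers no other protection. Caregiving that has ended biases mistreatment frequency in the programme's favour; the direction for partial changes is unknown.

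The plausible size is modest: a false-positive rate of about 0.06–0.09 against a nominal 0.05 if 3–6% stop caring and nothing else changes. It is higher only if net contact also falls among the rest. These figures assume that affected caregivers answer the follow-up survey and report no mistreatment, and that no care-status item sits in the attached forms. The true size cannot be computed from the documents.

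**What to change.** 1. Repeat the baseline weekly-hours and living-situation items in the follow-up survey.
2. Add one question on whether the participant is still caring for this person (yes / placed / died / other, with the date). Skip the mistreatment and care-quality scales if care has ended. This also spares bereaved caregivers those questions; Section 20.0 already lists guilt and embarrassment as risks.
3. In Section 17.0, state that the number no longer caring will be reported and that change in mistreatment and care quality will be analysed among those still caring. Describe change in weekly hours alongside. An hours-adjusted analysis would be imprecise with about 34 pairs and should be labelled exploratory.

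The cost is a few survey items, most already written for baseline, and possibly a few fewer pairs for the two distal outcomes. The entry criterion need not change for this purpose.
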